10.4.6 Analysis of secondary endpoints

Time to event outcomes including TTP, PFS and OS will be assessed with patients censored at time of last follow-up. TTP, PFS and OS rates of two patient groups will be estimated with the Kaplan-Meier method and compared between different groups using the log-rank test, respectively. The TTP, PFS and OS of each patient group at specific time points, such as 1 year, 3 years, and 5 years, etc. will be estimated alone with 95% CI. Cox proportional hazards models will be used in the multivariable analyses to assess adjusted effects of biomarkers on the patients' TTP, PFS and OS after adjusting for other factors. The proportional hazards assumption will be evaluated graphically and analytically with regression diagnostics.

Protocol therapy related toxicities rate will be summarized using descriptive statistics such as frequencies and proportions. Differences in the proportion of patients who experience protocol-related toxicities will not be compared between cohorts.

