5.3 Duration of follow-up

Patients will be followed for 4 weeks after removal from study and patient records will be reviewed until death or 2 years from enrollment (whichever comes first) to assess progression and survival. Patients removed from study for unacceptable adverse event(s) will be followed until resolution or stabilization of the adverse event.

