9. RESPONSE

Time to progression (TTP): Time to progression is defined as the time from last treatment until progression. Patients who have died without evidence of progression are censored in the TTP analysis at the time of death and patients who are alive without progression are censored at the last disease assessment.

Progression-Free Survival (PFS): Defined as the time from last treatment to the disease progression or death from any cause. Patients who have not progressed or died are censored at the date last known progression-free. Patients with no on-study assessment will be censored at the time of registration.

Overall survival (OS): OS is defined as the time from randomization to death. Alive patients are censored at the date last known alive.

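### Section 10.4.6 censors TTP and PFS at last follow-up, which contradicts Section 9 and would bias both rates upward wherever follow-up outlasts assessment for progression

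*Combined protocol and SAP*

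**What the plan says.** Section 10.4.6 (Analysis of secondary endpoints) opens with a single rule: "Time to event outcomes including TTP, PFS and OS will be assessed with patients censored at time of last follow-up". The Kaplan-Meier rates, the log-rank comparison of the two groups and the Cox models in that section all follow from it.

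Section 9 (Response) sets the rule separately for each endpoint:

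- TTP: "patients who are alive without progression are censored at the last disease assessment". For deaths, "Patients who have died without evidence of progression are censored in the TTP analysis at the time of death".
- PFS: "Patients who have not progressed or died are censored at the date last known progression-free", with a special case: "Patients with no on-study assessment will be censored at the time of registration".
- OS: "Alive patients are censored at the date last known alive".

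Section 5.3 (Duration of follow-up) says how long and for what purpose charts are read: "patient records will be reviewed until death or 2 years from enrollment (whichever comes first) to assess progression and survival". The tables in Section 6.5 (Schedule of events) place myeloma proteins at the first visit and at week 21 only, identically in both arms.

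**The concern.** The two sections give different censoring dates for the same patient, and no passage defines last follow-up or ranks one section over the other. Two analysts could each follow the document and produce different TTP and PFS curves.

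The difference has a direction. A patient whose disease was last assessed at one date, and who was last known alive at a later one, stays in the risk set through the interval under 10.4.6. A progression in that interval goes unseen, so the time counts as progression-free and the estimated rate rises. The sharpest case is a PFS patient with no on-study assessment, who contributes no time under Section 9 and the whole of follow-up under 10.4.6. At stake are the reported TTP and PFS rates, and the analyses that use the same times: the log-rank tests, the biomarker Cox models and the peak-HAI-by-PFS analysis in Section 10.4.5.

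**Working it through.** The documents state no TTP or PFS rate, so there is no figure to reproduce. The rules were set side by side, and the effect was then sized under stated assumptions.

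**Step 1: the rules compared**

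| Patient | Section 9 | Section 10.4.6 | Same date? |
|---|---|---|---|
| TTP, alive, no progression | last disease assessment | last follow-up | only if last follow-up was an assessment |
| TTP, died without progression | death | last follow-up | yes, if follow-up ends at death |
| PFS, alive, no progression | date last known progression-free | last follow-up | only if progression was reviewed then |
| PFS, no on-study assessment | registration | last follow-up | no |
| OS, alive | date last known alive | last follow-up | yes, in substance |

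**Step 2: can the dates differ here?** The last scheduled myeloma protein test is at week 21, which is 20 × 7 = 140 days after week 1. Records are reviewed to 2 years, or 730 days. The longest gap after the last scheduled test is therefore 730 − 140 = 590 days. Section 10.3 also reports that 27 of the first 50 patients missed the week 21 study assessment, which is 27/175 = 15% of planned consents. Some of them may have had routine tests, so this does not measure the unassessed share.

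**Step 3: size by formula.** Assumptions not in the documents:

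- Progression is exponential with rate λ.
- A share f is not assessed after day 140 but is followed to day 730, and all later progressions in that share are missed.
- There are no deaths, and the clock starts at enrolment for everyone.

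The 2-year rate read under 10.4.6 is then

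S(730) = (1 − f)·exp(−730λ) + f·exp(−140λ), against a true rate of exp(−730λ).

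For a median of 24 months, λ = ln 2/730, so exp(−730λ) = 0.500 and exp(−140λ) = 0.876.

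- f = 0.1: 0.9 × 0.500 + 0.1 × 0.876 = 0.538
- f = 0.3: 0.7 × 0.500 + 0.3 × 0.876 = 0.613

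The same formula gives 44–53% against a true 40% (median 18 months) and 66–72% against a true 63% (median 36 months).

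**Step 4: simulation with deaths.** Each scenario had 400,000 patients. The assumptions were exponential progression, a death hazard of 0.004 per month, vital status to 24 months, and a share f last assessed at week 21. The 24-month rates (%) at f = 30% were:

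| Median (months) | TTP true | TTP 10.4.6 | TTP Section 9 | PFS true | PFS 10.4.6 | PFS Section 9 |
|---|---|---|---|---|---|---|
| 18 | 39.9 | 52.8 | 40.5 | 36.2 | 48.0 | 35.1 |
| 36 | 63.1 | 71.5 | 63.5 | 57.3 | 65.0 | 55.6 |
| 60 | 75.9 | 81.5 | 76.2 | 69.0 | 74.1 | 66.9 |

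Across medians, the 24-month excess under 10.4.6 was:

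- f = 0: 0 points
- f = 10%: 1.9–4.3 points for TTP and 1.7–3.9 for PFS
- f = 50%: 9.4–21.6 points for TTP and 8.5–19.6 for PFS

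**Step 5: arms.** Section 9 starts TTP and PFS at last treatment. If that means the last study vaccination (an assumption), time zero is week 17 in the experimental arm and week 1 in control, so week 21 falls 28 and 140 days later. With a 24-month median and f = 30% in both arms, the true 1-year rate is exp(−365λ) = 0.707. The excess is 0.3 × (0.974 − 0.707) = 0.080 in the experimental arm and 0.3 × (0.876 − 0.707) = 0.051 in control.

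**The case against.** The strongest reply is Section 5.3. The record review to 2 years is expressly meant to assess progression as well as survival. The schema also lists myeloma proteins among standard-of-care tests, so charts may hold results after week 21. If last follow-up means the last review at which progression was looked for, the two sections give the same date for most patients and the bias is zero. This stands. A reader might infer that the rates *are* inflated; the documents support only that they *would be*, where follow-up outlasts assessment. The reply does not remove the contradiction, because last follow-up is undefined, and it does not reconcile the PFS registration rule.

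A reader might also take the schedule's footnote on the modified myeloma assessment to mean that the week 21 test is optional. That footnote is conditioned on results being unavailable within 30 days of the first vaccination and reads most naturally as covering baseline, so nothing here rests on it.

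A further inference is that the comparison of arms is biased. The documents schedule disease assessment and PFS/OS collection identically in both arms, and nothing indicates different follow-up. Step 5 shows that equal gaps could still act unequally, but only under one reading of last treatment and an assumed f.

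Nor is Section 9 the exact truth. In the simulation its TTP was within about 1.3 points, but its PFS ran from 0 to about 5 points low, because later deaths still count while assessed time is cut back.

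Finally, TTP, PFS and OS are absent from the objectives in Sections 1 and 2, and a careful statistician would probably follow Section 9. That limits the weight of the point. It does not make the sentence in the analysis section right.

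**Conclusion.** The point holds as a contradiction between a stated analysis rule and the endpoint definitions. Taken literally, 10.4.6 would bias TTP and PFS upward where follow-up outlasts assessment for progression, most sharply for PFS patients with no on-study assessment. OS is consistent between the two sections.

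The size cannot be read from the documents. It is zero if every last follow-up includes a progression review. Under the assumptions of Step 3 with a 24-month median, a true 50% at 2 years would read about 54–61%. The 10–30% share and the progression rates are assumptions. Distortion of the arm comparison is possible but not shown. The primary week-21 seroprotection analysis and its sample size are unaffected. The correction should be made, but it does not threaten the trial's main conclusion.

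**What to change.** Replace the first sentence of Section 10.4.6 with: *TTP, PFS and OS will be censored as defined for each endpoint in Section 9.*

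A plain cross-reference is better than writing one new date for TTP and PFS together. A sentence that moved both to the last disease assessment would lose three Section 9 rules: TTP censoring at death without progression, the PFS date last known progression-free, and PFS censoring at registration.

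The cost is one sentence and no new data. TTP and PFS rates may be less favourable, and numbers at risk will fall earlier. The change should be made before the time-to-event data are analysed, so that the rule is not chosen after the curves are seen.

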7.1.5 Expected adverse events / toxicities

Adult recipients of inactivated influenza virus vaccines may develop influenza-like reactions such as fever, feverishness (chills/shivering/sweating), gastrointestinal side effects (emesis and diarrhea), fatigue (tiredness), malaise (general unwell feeling), myalgia (body aches/muscular pain), arthralgia (joint pain), headache, and/or nausea. Some subjects may develop reactions at the injection site, including pruritus (itching), ecchymosis (bruising), erythema (redness), induration (hardness)/swelling, pain, and/or tenderness. With unadjuvanted licensed, inactivated influenza virus vaccines most of these reactions peak in intensity in the first 24 hours after vaccination and usually disappear without treatment within 1 or 2 days. Analgesics (e.g., acetaminophen, or ibuprofen or similar non-steroidal anti-inflammatory drugs (NSAIDs)) and rest may generally relieve or lessen these reactions. Bruising can sometimes occur due to the vaccination procedure.

In addition, post-marketing surveillance indicates the following adverse events of special interest (AESI) as potential risks for pandemic vaccines based on those identified for the seasonal influenza vaccines: neuritis, convulsions, severe allergic reactions, encephalitis, thrombocytopenia, vasculitis, and Guillain-Barré (GBS) syndrome. Reports of these reactions were rare; however, exact incidence rates cannot be precisely calculated.

Acute and potentially life-threatening allergic reactions are also possible. Very rarely, occurring in about 1 in 4 million people given a vaccination, there can be a serious allergic reaction to a vaccine. These reactions can manifest as skin rash (hives), swelling around the mouth, throat or eyes, difficulty breathing, a fast pulse, or loss of blood pressure. If these reactions occur, they can usually be stopped by the administration of emergency medications by the study personnel. As with any vaccine or medication, there is a very small chance of a fatal reaction (death), although researchers do not expect this to occur.

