10.4.2 Safety analyses

Adverse event data will be described and graded per the NCI CTCAE guidelines. For each adverse event, information to be collected includes event description, time of onset, clinician assessment of severity, relationship to study product (assessed only by those with the training and authority to make a diagnosis), and time of resolution/stabilization of the event. All vaccine-related AEs will be recorded with start dates occurring any time after patient receives any study drug until 7 (for non-serious AEs) or 100 days (for SAEs) after the last day of study participation. At each study visit, the investigator will inquire about the occurrence of AE/SAEs since the last visit. Events will be followed for outcome information until resolution or stabilization.

Any medical condition that is present at the time that the participant is screened will be considered as baseline and not reported as an AE. However, if the study participant's condition deteriorates at any time during the study, it will be recorded as an AE. Changes in the severity of an AE will be documented to allow an assessment of the duration of the event at each level

of severity to be performed. AEs characterized as intermittent require documentation of onset and duration of each episode.

The maximum grade for each type of toxicity will be recorded for each patient, and frequency tables will be reviewed to determine toxicity patterns. Adverse events will be summarized and described within each cohort. They will initially be reviewed regardless of attribution, but also whether they are possibly, probably, or definitely related to treatment. In addition, we will review all adverse event data that are graded as 3, 4, or 5 and classified as either “unrelated” or “unlikely to be related” to study treatment in the event of an actual relationship developing. The incidence of severe adverse events or toxicities will be described. We will assess the proportion of patients who experience grade 3 or higher non-hematologic toxicity. To assess tolerability, we will also capture the proportion of patients who go off treatment due to adverse events.

Temporary suspension of enrollment [due to toxicity \(aka stopping rules\) are described elsewhere.](#)

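### The plan gives no between-arm estimate of vaccine toxicity and no by-dose summary, so the burden of doses 2 and 3 is only described arm by arm

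*Combined protocol and SAP*

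**What the plan says.** Section 10.4.6 plans "Protocol therapy related toxicities rate will be summarized using descriptive statistics such as frequencies and proportions" and then adds: "Differences in the proportion of patients who experience protocol-related toxicities will not be compared between cohorts". The word cohort is not defined. Section 10.2 analyses safety by the cohort in which a patient was enrolled, and I read it as randomised arm.

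Section 10.4.2 sets out the summary: "The maximum grade for each type of toxicity will be recorded for each patient, and frequency tables will be reviewed to determine toxicity patterns". It continues: "Adverse events will be summarized and described within each cohort". Two proportions are named: "We will assess the proportion of patients who experience grade 3 or higher non-hematologic toxicity" and "To assess tolerability, we will also capture the proportion of patients who go off treatment due to adverse events". Neither section plans a difference, a confidence interval or a table by dose number.

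On collection, the notes to the schedule in section 6.5 call for vaccine-related events to be assessed on the day of each Fluzone HD dose and 7 days after it. The schedule records grade 2 or higher events at three vaccination visits in the experimental arm and at one in the control arm. Section 10.4.2 also asks for onset, resolution, changes in severity and each episode of an intermittent event.

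**The concern.** The two extra injections are the intervention (sections 6.1.1 and 6.1.2). Section 3.8.1 lists extra influenza vaccination among the study risks. Section 3.5 says that replicating the earlier two-dose trial should lead to a change in practice. A decision of that kind sets the gain in seroprotection against the added burden of the schedule, and each needs an estimate with its uncertainty. The plan supplies this for the gain and rules it out for the burden.

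The question particular to repeat dosing is whether reactions come back or get worse at doses 2 and 3. A highest grade per toxicity type over the whole study cannot show that.

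**Working it through.** **1. The plan's own figures.** No precision or power is stated for toxicity, so there is no toxicity figure to reproduce. The patient numbers come from section 10.3, and those do reproduce. For logistic regression on a balanced binary covariate with rates 0.333 and 0.585, the mean rate is P = 0.459 and

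N = [1.96·√(P(1−P)/0.5) + 0.8416·√(0.333·0.667 + 0.585·0.415)]² / [(0.252)²·0.5] = 120.4.

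Dividing by 1 − 0.1 for the R-squared gives 133.8, against the stated 134 (67 per arm). The plan enrols 74 per arm after dropout.

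**2. Patients available for safety.** I use 74 per arm. An upper bound is 175/2 = 87.5, taken as 87, because the title page gives 175 consented patients. It is only an upper bound: the safety set in section 10.2 requires eligibility and at least one dose.

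**3. Precision of a between-arm difference.** Half-width = 1.96·√[(p₁(1−p₁) + p₂(1−p₂))/n]. The rates are assumptions.

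- 5% v 10%, n = 74: 1.96·√(0.1375/74) = 0.084, or 8.4 points. With n = 87: 7.8 points.
- 10% v 20%, n = 74: 1.96·√(0.25/74) = 0.114, or 11.4 points. With n = 87: 10.5 points.

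The only usable rate in the documents is injection-site soreness at 10–64% (section 3.8.1). With equal rates in both arms and n = 74, 1.96·√(2p(1−p)/74) gives 9.7 points at 10% and 15.5 points at 64%. Only events of grade 2 or higher are scheduled for recording, so the recorded rate may be lower.

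**4. Zero events.** The upper 97.5% limit is 1 − 0.025^(1/n): 4.9% at n = 74 and about 4.2% at n = 87.

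**5. What repeat dosing might add.** Assume a constant, independent risk per dose, so that the three-dose risk is 1 − (1−p)³, with n = 74.

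- p = 10%: 27.1% against 10%, a difference of 17.1 points, half-width 12.2, power 77%.
- p = 2%: 5.9% against 2%, a difference of 3.9 points, half-width 6.2, power 23%.

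An interval would separate the arms in the first case and not in the second.

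**6. What the highest-grade summary loses.** A patient with grade 2 fatigue after all three doses and one with grade 2 fatigue after dose 1 only produce the same entry. So do a patient who goes from grade 2 at dose 1 to grade 3 at dose 3 and a patient with a single grade 3 event at dose 1.

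**7. Whether a by-dose table is possible.** Onset dates and a 7-day assessment after each dose are already required, so each event can be assigned to a dose without new collection.

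**The case against.** The best defence is that the trial is sized only for seroprotection, so declining to test toxicity is reasonable, and per-arm counts will let any reader compute a difference. The first half stands as an argument against a hypothesis test. It does not justify ruling out an estimate: the same section 10.4.6 plans log-rank comparisons of TTP, PFS and OS between groups, for which the trial is not sized either. The second half shows how small the change is.

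A reader might be tempted by four stronger claims that the documents do not support.

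- *Toxicity is reduced to one grade per patient.* It is not. Section 10.4.2 keeps the highest grade for each type, so the kind of reaction survives. Recurrence and dose number are lost.
- *The trial cannot speak to tolerability, or cannot separate the doses.* Per-arm proportions, severe events and withdrawals for adverse events are all planned, and events are dated. What is missing is the analysis.
- *Randomisation would make the difference free of bias.* The blinding items in section 10.5 are marked not applicable. Attribution rests on clinician judgment (section 11.3), and section 11.1 captures only events related to vaccination or influenza-like illness. The experimental arm has three recording windows against one, so background symptoms at weeks 9 and 17 can be counted in one arm alone. Serious events are less exposed to this, since both arms have the same contacts about them at weeks 5, 9, 17 and 21.
- *Blood toxicity is ignored.* One named proportion excludes hematologic events, although section 7.1.5 lists thrombocytopenia among "neuritis, convulsions, severe allergic reactions, encephalitis, thrombocytopenia, vasculitis, and Guillain-Barré (GBS) syndrome". The remaining summaries in section 10.4.2 carry no such exclusion, and events of special interest are reported to the manufacturer (section 11.6.1). The firmer limit is that the blood count is scheduled only before vaccination, so hematologic events would be found incidentally.

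**Conclusion.** The concern holds as a reporting gap. The plan expressly rules out comparing toxicity between arms and has no by-dose summary, so a trial meant to change practice would describe the added burden of doses 2 and 3 without estimating it. The sample would support an interval of roughly ±8 to ±11 points for reactions in the 5–20% range. That is informative for common reactions and weak for rare or severe ones. These figures rest on assumed event rates, on 74 to 87 dosed patients per arm, and on reading cohort as arm. The primary analysis is unaffected. This is a cheap improvement worth making.

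**What to change.** Replace the sentence in section 10.4.6 with: *The between-arm difference in the proportion of patients with any grade ≥2, and any grade ≥3, vaccine-related adverse event will be reported with a 95% CI, without a hypothesis test.*

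In section 10.4.2, add a table of these events in the 7-day window after each Fluzone HD dose. Use the number of patients receiving that dose as the denominator, and show dose 1 for both arms. The dose 1 columns are the like-for-like comparison, because both arms have that window.

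State the limits beside the results:

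- attribution is open-label;
- the experimental arm has three recording windows and the control arm one;
- recipients of doses 2 and 3 are selected, since section 5.2 names a grade 3 event within 7 days of the first dose as a ground for leaving the study in the experimental arm;
- hematologic events are detected only incidentally.

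The cost is a change of wording and a few table columns, with no new data. The drawback is wide intervals for rare events.

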10.5 Measure to minimize bias

10.5.1 Randomization

The total sample size of 148 patients will be split equally between the arms.

